# 16.7 Week 10 Day 1 ( $\pm$ 3 days)

At Week 10 Day 1, patients will return to the clinic to receive pembrolizumab and undergo the following procedures:

- 1. AE monitoring
- 2. Recording of concomitant medications
- 3. Vital signs and weight
- 4. Symptom-directed physical exam

- 5. ECOG Performance Status
- 6. Clinical laboratory evaluation (hematology, serum chemistry, urinalysis, coagulation).
- 7. Research blood collection. (including blood sample for Flt-3L level monitoring)
- 8. Optional post-baseline tumor biopsy. Coagulation tests must be performed and evaluated within 24 hr prior to all biopsy procedures.
- 9. Radiographic evaluation of tumor burden and determination of response by RECIST v1.1 and iRECIST. See Appendices 5 and 6.
- 10. Administration of pembrolizumab. For the purposes of this study, pembrolizumab should be administered *after* the GX-188E vaccination on all days in which patients are scheduled to receive both.

# 16.8 Week 13 Day 1 ( $\pm$ 3 days)

At Week 13 Day 1, patients will return to the clinic for administration of GX-188E + P and undergo the following procedures:

- 1. AE monitoring
- 2. Recording of concomitant medications
- 3. Vital signs and weight
- 4. Symptom-directed physical exam
- 5. ECOG Performance Status
- 6. Clinical laboratory evaluation (hematology, serum chemistry, *and both blood CEA/TA4 levels and thyroid function tests*).
- Pain Assessment. Within 30 minutes before and 5 minutes (± 2 minutes) after GX-188E administration, pain score in association with the electroporation (EP) procedure should be reported.
- 8. Administration of GX-188E at both right and left deltoid muscles (or, lateralis muscles for Reduction Level 1)

9. Administration of pembrolizumab. For the purposes of this study, pembrolizumab should be administered *after* the GX-188E vaccination on all days in which patients are scheduled to receive both.

# 16.9 Week 16 Day 1 ( $\pm$ 3 days)

Patients will return to the clinic to receive pembrolizumab. Standard-of-care safety procedures are required only as clinically indicated and per institutional standards of care in association with usual pembrolizumab administration. Only clinically significant abnormalities will be reported into the database and noted as adverse events.

- 1. AE monitoring
- 2. Recording of concomitant medications
- 3. Vital signs and weight
- 4. Symptom-directed physical exam
- 5. ECOG Performance Status
- 6. Clinical laboratory evaluation (hematology and serum chemistry).
- 7. Research blood collection
- 8. Pembrolizumab administration. For the purposes of this study, pembrolizumab should be administered *after* the GX-188E vaccination on all days in which patients are scheduled to receive both.

### Pembrolizumab will continue to be administered once every 3 weeks.

Blood CEA/TA4 levels and thyroid function tests will be performed approximately every 6 weeks for the duration of study participation.

Research blood will be collected further at Week 22, Week 49, and every 27 weeks thereafter. (Including blood sample for Flt-3L level monitoring). Research blood collections are not performed on Day 1 of Week 103 visit but at the EOS visit.

# 16.11.1 Every 3 Weeks (after Week 19 Day 1)( $\pm$ 3 days)

After Week 19 Day 1, patients will return to the clinic to receive pembrolizumab. Standard-of-care safety procedures are required only as clinically indicated and per institutional standards

of care in association with usual pembrolizumab administration. Only clinically significant abnormalities will be reported into the database and noted as adverse events. The last dose of Pembrolizumab would be administered on Week 103 Day 1 and patients will undergo the following procedures.

- 1. AE monitoring
- 2. Recording of concomitant medications
- 3. Vital signs and weight
- 4. Symptom-directed physical
- 5. Clinical laboratory evaluation (as indicated; only clinically significant findings will be reported).
- 6. Pembrolizumab administration

# 16.11.2 Every 9 Weeks (after Week 19 Day 1) ( $\pm$ 1 week)

Approximately every 9 weeks after Week 19 Day 1, patients will return to the clinic to undergo the following procedures:

- 1. AE monitoring
- 2. Recording of concomitant medications
- 3. Vital signs and weight
- 4. Symptom-directed physical exam
- 5. ECOG Performance Status
- 6. Clinical laboratory evaluation (hematology, serum chemistry).
- 7. Radiographic evaluation of tumor burden and determination of response by RECIST v1.1 and iRECIST. See Appendices 5 and 6.

In accordance with the standard administration schedule (i.e. every 3 weeks), pembrolizumab will also be administered at these visits as appropriate.

# 16.11.3 Week 46 Day 1 (± 1 week, GX-188E optional administration)

At Week 46 Day 1, patients will return to the clinic to receive undergo the following procedures:

1. AE monitoring

- 2. Recording of concomitant medications
- 3. Vital signs and weight
- 4. Symptom-directed physical exam
- 5. ECOG Performance Status
- 6. Clinical laboratory evaluation (hematology, serum chemistry).
- 7. An optional GX-188E administration may be given at week 46 if it is in the best interests of the patient, as determined by the investigator, once the patient has completed 37 weeks of treatment. Additional GX-188E administration(s) may be given to the subject after discussion with the sponsor. (Optional) Pain Assessment. Within 30 minutes before and 5 minutes (± 2 minutes) after GX-188E administration, pain score in association with the electroporation (EP) procedure should be reported.
- 8. (Optional) Administration of GX-188E at both right and left deltoid muscles (or, lateralis muscles for Reduction Level 1)

In accordance with the standard administration schedule (i.e. every 3 weeks), pembrolizumab will also be administered as appropriate. For the purposes of this study, pembrolizumab should be administered *after* the GX-188E vaccination on all days in which patients are scheduled to receive both.

# 16.12 End of Study (EOS)

The End of Study (EOS) visit must occur within 28 days of treatment discontinuation / completion (Week 103 Day 1) and prior to initiation of any new anti-cancer therapy/regimen. All patients discontinuing study treatment for any reason should undergo the following EOS procedures:

- 1. AE monitoring
- 2. Recording of concomitant medications
- 3. Vital signs and weight
- 4. Complete physical examination
- 5. ECOG performance status evaluation

- 6. Clinical laboratory values (hematology, coagulation, chemistry, urinalysis, *and both blood CEA/TA4 levels and thyroid function tests*)
- 7. Serum or urine pregnancy test for women of child-bearing potential
- 8. Research blood collection
- 9. Optional post-baseline tumor biopsy (only requested for patients with biopsy-accessible lesions and who discontinue from study prior to Week 10). Coagulation tests must be performed and evaluated within 24 hr prior to all biopsy procedures.
- 11. Radiographic evaluation of tumor burden and determination of response by RECIST v1.1 and iRECIST. See Appendices 5 and 6. Note: This is not required if confirmed PD is the reason for study discontinuation.

# 16.13 Long-Term Follow-Up

Patients will enter into the long-term follow-up phase of the study after the EOS visit to obtain survival data. Survival data may be obtained either by clinic visit or by remote communication (e.g., telephone call or email) or hospital medical records. Sites must follow up with patients approximately every 4 months for up to 1 year to obtain the following data:

- Survival status: Is the patient still living? (Yes or No)
  - o If "No", what was the approximate date of death?
- Has the patient received any subsequent active anti-cancer treatment (this does not include palliative measures)? (Yes or No)
  - o If "Yes", what treatments has the patient received?

Family members, primary care giver, public records, or primary treating oncologist/oncologist's office may confirm a patient's death.

# 17.0 Patient Identification and Tracking

Each patient will be assigned a unique number and will keep this number for the duration of the study. Patient numbers will not be reassigned or reused for any reason. Patients should be identified to the Sponsor only by their assigned number, initials, date of birth, and sex. The Investigator must maintain a patient master log.

#### 18.0 Screen Failures

Patients who sign an informed consent form but who do not meet all inclusion and exclusion criteria and who do not receive any part of the investigational treatment regimen, are defined as Screen Failures. For all screen failures, the Investigator (or designee) will record the screening number, patient initials, and reason(s) for screen failure into the Screen Fail Log. These data will be retained in the Investigator's study files, reviewed for completeness and collected at the end of the study.

#### 19.0 Discontinuation/Withdrawal criteria

# 19.1 **Discontinuation of Study Treatment**

Discontinuation of study treatment does not represent withdrawal from the study.

A participant must be discontinued from study treatment but continue to be monitored in the study for any of the following reasons:

- Recurrent Grade 2 pneumonitis
- Discontinuation of treatment may be considered for participants who have attained a confirmed complete response (CR) and have been treated for at least 8 pembrolizumab cycles (at least 24 weeks), including 2 doses of pembrolizumab beyond the date when the initial CR was declared.
- Completion of 35 treatments (approximately 2 years) with pembrolizumab. Note: The number of treatments is calculated starting with the first dose of pembrolizumab.

The reasons a patient may discontinue or be withdrawn from the study include, but are not limited to, adverse events, disease progression, patient request, Investigator decision, protocol violation, patient noncompliance, and study termination by the Sponsor.

When a patient discontinues or is withdrawn, the Investigator will notify the Sponsor (or designee) and should perform the procedures indicated in the EOS column in the Schedule of Events (Appendix 1) within 28 days after discontinuation of study drug and prior to initiation of any therapy.

#### 20.0 SAFETY REPORTING AND DOCUMENTATION OF CLINICAL RESULTS

# 20.1 Safety Evaluations

For safety information on GX-188E, refer to the most recent version of the Investigator's Brochure. For safety information on pembrolizumab, please refer to the package inserts.

Routine safety and tolerability will be evaluated from the results of reported signs and symptoms, scheduled physical examinations, vital sign measurements, and clinical laboratory test results.

More frequent safety evaluations than required by this protocol may be performed if clinically indicated and at the discretion of the Investigator. All adverse events (AEs) will be recorded from the time the patient receives the first dose of the investigational treatment regimen to 28 days after the last dose.

#### 20.1.1 **Physical Examination**

Complete physical examinations will be performed by a licensed physician (or physician's assistant or nurse practitioner) at Screening and End of Treatment. Symptom-directed physical exam are required at each clinical visit and as clinically indicated. Please refer to the Schedule of Events (Appendix 1).

# 20.1.2 Vital Signs

Vital signs (blood pressure, respiratory rate, pulse rate, and temperature) will be obtained in the sitting position. All patients should be sitting for 3-5 min prior to obtaining vital signs. Please refer to the Schedule of Events (Appendix 1).

# 20.1.3 Safety Laboratory Determinations

Laboratory evaluations, including complete blood count with differential, comprehensive chemistry panel, coagulation tests, thyroid function tests, and urinalysis, will be performed as noted in the Schedule of Events (Appendix 1).

#### 20.1.4 Pain Assessment

On each GX-188E vaccination day, Pain Assessment Monitoring will be performed within 30 minutes before and 5 minutes (± 2 minutes) after the vaccination procedure using a 0-10 numeric pain rating scale (Figure 4).

[figure not shown]

Figure 4. Numeric Pain Rating Scale

# 20.2 Adverse Events (AE)

The Investigator will evaluate all adverse events (AEs) according to the NCI Common Terminology Criteria for Adverse Events Version 4.0 or the most recent version. An **adverse event** (AE) is any untoward, undesired, or unplanned event in the form of signs, symptoms, disease, or laboratory or physiologic observations occurring in a person given a test article in a clinical study. The event does not need to be causally related to the investigational treatment. An AE includes, but is not limited to, the following:

- Any clinically significant worsening of a preexisting condition
- An AE occurring from overdose (i.e., a dose higher than that indicated in the protocol) of a test article, whether accidental or intentional
- An AE occurring from abuse (e.g., use for nonclinical reasons) of a test article
- An AE that has been associated with the discontinuation of the use of a test article

Any treatment-emergent abnormal laboratory result which is clinically significant, i.e., meeting one or more of the following conditions, should be recorded as a single diagnosis on the adverse event page in the CRF:

- Accompanied by clinical symptoms
- Leading to a change in study medication (e.g., dose modification, interruption, or permanent discontinuation)

• Requiring a change in concomitant therapy (e.g., addition of, interruption of, discontinuation of, or any other change in a concomitant medication, therapy or treatment)

Clear progression of the patient's primary malignancy should not be reported as an AE, unless it results in hospitalization or death. Findings that are clearly consistent with the expected progression of the underlying cancer should not be reported as an adverse event, and hospitalizations due to the progression of cancer do not necessarily qualify for an AE. If there is any uncertainty about a finding being due solely to progression of primary malignancy, the finding should be reported as an AE as appropriate.

AEs should be considered treatment-related, unless they fulfill the following criteria:

- Evidence exists that the AE has an etiology other than the investigational product (e.g., preexisting medical condition, underlying disease, intercurrent illness, or concomitant medication), and/or
- The AE has no plausible temporal relationship to administration of the investigational product (e.g., a new cancer diagnosed 2 days after first dose of study drug).

Relatedness to study medication will be graded as either, "probably", "possibly", "unlikely", or "unrelated" as follows:

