# 16.4 Week 3 Day 1 (±3 days)

Only safety evaluations will occur at the Week 3 Day 1 visit; no study drugs will be administered. Patients will undergo the following procedures on Week 3 Day 1:

- 1. AE monitoring
- 2. Recording of concomitant medications
- 3. Vital signs and weight
- 4. Symptom-directed physical exam
- 5. Clinical laboratory evaluation (hematology and serum chemistry).

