#### 21.0 **Dose-Limiting Toxicities (DLTs)**

All toxicities will be graded using NCI-CTCAE Version 4.0 or the most recent version based on the investigator assessment.

The DLT window of observation will be during Cycle 1 of pembrolizumab (ie., the first 3 weeks of treatment prior to Week 4 Day 1 visit). A DLT is defined as any AE that is not clearly due to progression of the patient's primary malignancy, occurs within the DLT window of observation period, and that meets at least one of the criteria below:

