### Hematologic Dose Limiting Toxicities:

- Grade 4 neutropenia (ANC  $< 0.5 \times 10^9/L$ )
- Grade 3 febrile neutropenia (ANC <  $1.0 \times 10^9$ /L with temperature  $\ge 38.3$ °C)
- Grade 4 thrombocytopenia (platelet count  $< 25.0 \times 10^9/L$ ) lasting > 4 days or that requires platelet transfusion
- Grade  $\geq$  3 thrombocytopenia (platelet count < 50.0 x 10^9/L) associated with Grade  $\geq$  3 bleeding

• Any hematologic toxicity resulting in death (i.e. Grade 5)

In addition, any other AE that is felt to be treatment-limiting in the medical opinions of the Principal Investigator and the Sponsor's Medical Monitor may be considered a DLT. These include, but are not limited to the following:

- Any toxicity leading to more than one missed dose of either GX-188E or pembrolizumab during the DLT-evaluation period
- Any toxicity leading to > 2 weeks delay in initiation of the  $2^{nd}$  cycle of pembrolizumab

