#### 16.1.7. DOSE LIMITING TOXICITY (DLT)

A DLT is defined as any AE that is not clearly due to progression of the patient's primary malignancy, occurs within the DLT window of observation period, and that meets at least one of the criteria below:

Non-Hematologic Dose Limiting Toxicities:

Any CTCAE (v4 or the most recent version) AE of ≥ Grade 3 treatment-related non-hematological toxicity except for the following:

o nausea, vomiting, or diarrhea lasting ≤ 72 hr

o Grade 3 fatigue lasting ≤ 7 days

o hypersensitivity reactions lasting ≤ 72 hrs

o Grade 3 hyperglycemia lasting ≤ 72 hr with standard anti-diabetic therapy

o Grade 3 increases in liver transaminases in patients with liver metastases. (Note: Grade 4 increases in LFTs in any patient will be considered a DLT)

o clinical laboratory abnormalities that are reversible to ≤ Grade 1 or baseline status within 72 hr with outpatient care and/or monitoring, or that are considered not clinically significant by the Principal Investigator

Hematologic Dose Limiting Toxicities:

o Grade 4 neutropenia (ANC < 0.5 x10^9/L)

o Grade 3 febrile neutropenia (ANC < 1.0 x 10^9/L with temperature ≥ 38.3°C)

o Grade 4 thrombocytopenia (platelet count <  $25.0 \times 10^9$ /L) lasting > 4 days or that requires platelet transfusion

o Grade  $\geq$  3 thrombocytopenia (platelet count < 50.0 x 10 $^{9}$ /L) associated with Grade  $\geq$  3 bleeding

o Any hematologic toxicity resulting in death (i.e. Grade 5)

In addition, any other AE that is felt to be treatment-limiting in the medical opinions of the Principal Investigator and the Sponsor's Medical Monitor may be considered a DLT. These include, but are not limited to the following:

Author: [name] Version Number: 1.1

Version Date: 05Sep2022

Template No: CS\_TP\_BS016 Revision 6 Reference: CS\_WI\_BS005

Effective Date: 02Dec2019

Analysis Plan Page 38 of 48

o Any toxicity leading to more than one missed dose of either GX-188E or pembrolizumab during the DLT-evaluation period

o Any toxicity leading to > 2 weeks delay in initiation of the 2nd cycle of pembrolizumab.

The DLT window of observation will be during Cycle 1 of pembrolizumab (ie., the first 3 weeks of treatment prior to week 4 Day 1 visit).

A DLT will be identified on "Adverse Events" form of CRF with the response of "Yes" to the question "Is this AE considered as a DLT (Dose-Limiting Toxicities)?".

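### Two hematologic DLT criteria rest on laboratory values alone, but Section 20.2 does not require such values on the AE page from which the SAP counts DLTs, so the reported Part A DLT incidence could be too low

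*Protocol*

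**What the plan says.** **Recording rule (Protocol 20.2).** "Any treatment-emergent abnormal laboratory result which is clinically significant, i.e., meeting one or more of the following conditions, should be recorded as a single diagnosis". That entry belongs to the AE page of the CRF. Three conditions follow. The first is "Accompanied by clinical symptoms"; the second is "Leading to a change in study medication (e.g., dose modification, interruption, or permanent discontinuation"); the third is "Requiring a change in concomitant therapy". Neither CTCAE grade nor a Section 21 threshold is among them.

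**DLT definition (Protocol 21.0).** "A DLT is defined as any AE that is not clearly due to progression of the patient's primary malignancy", that falls in the first three weeks and meets a listed criterion. The first hematologic criterion begins "Grade 4 neutropenia (ANC" and gives a limit of 0.5 × 10^9/L, with no symptom, duration or treatment condition. The exemption for laboratory findings judged not clinically significant stands only in the non-hematologic list.

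**Counting rule (SAP 16.1.7).** "A DLT will be identified on 'Adverse Events' form of CRF", by a Yes to the DLT question there. No other source is named. The safety monitoring plan in the synopsis likewise has the Safety Monitoring Committee decide which AEs are DLTs.

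**Data in the window (Protocol 16.3 and 16.4).** Hematology is drawn at Week 2 and Week 3. On the latter visit: "Only safety evaluations will occur at the Week 3 Day 1 visit; no study drugs will be administered".

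**The concern.** The rule for what is written down and the rule for what is counted do not meet. A value can satisfy Section 21 and none of the three conditions in Section 20.2. The only instruction specific to laboratory results then does not call for an AE entry, and without an entry there is no box to tick.

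DLT incidence is the Part A primary endpoint (Protocol 24.1). DLT status also decides which Part A patients join the first stage of Part B, because Sections 10.2 and 24.3 admit only those without a DLT. SAP 16.3.2 grades all laboratory values by CTCAE but does not link the grades to DLT status. The report could therefore show a Grade 4 neutrophil count inside the window and no corresponding DLT, with nothing in the plan to flag it.

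**Working it through.** **Step 1. Which hematologic criteria can be met without triggering Section 20.2?**

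| Section 21 criterion | Non-laboratory element | Can escape the 20.2 conditions? |
|---|---|---|
| Grade 4 neutropenia | none | yes |
| Grade 3 febrile neutropenia | fever | no (symptom) |
| Grade 4 thrombocytopenia, more than 4 days | none; serial values only | yes |
| Grade 4 thrombocytopenia, transfused | transfusion | no (treatment change) |
| Grade ≥3 thrombocytopenia with Grade ≥3 bleeding | bleeding | no |
| Hematologic death | death | no |

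The gap is confined to one criterion and one limb of another. Grade 4 anemia is not a listed hematologic DLT.

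**Step 2. A concrete case.** ANC is below 0.5 × 10^9/L at Week 3, without fever or growth factor, and has recovered by Week 4. It meets Section 21. There is no symptom, no dose is due at that visit to be changed, and no concomitant treatment changes. Section 20.2 does not require an entry, so the SAP has no DLT to count.

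**Step 3. Effect on reported incidence.** One omitted event lowers it by 1/6 = 16.7 percentage points in 6 patients or 1/9 = 11.1 points in 9.

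**Step 4. Sensitivity of the 6+3 rule (context only).** The plan states no pass probability to reproduce. A schedule passes with 0 or 1 DLT in 6, or with 2 in 6 and none in 3 more:

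P(pass) = (1−p)^6 + 6p(1−p)^5 + 15p²(1−p)^4 × (1−p)^3

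At p = 0.33: 0.0905 + 0.2673 + 0.0990 = 0.457. If a share m of DLTs goes unrecorded, p is replaced by p(1−m). The documents give no value for m, so the range is an assumption:

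| True DLT rate | m = 0 | m = 10% | m = 25% | m = 50% |
|---|---|---|---|---|
| 33% | 45.7% | 53.9% | 66.5% | 85.6% |
| 20% | 78.1% | 82.6% | 88.5% | 95.8% |

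These figures show how much the rule depends on full capture. They do not bear on any decision still open.

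**Step 5. What the draws can show.** Week 2 Day 1 is study day 8 and Week 3 Day 1 is day 15, each ±3 days. The two draws can therefore be from 12 − 11 = 1 to 18 − 5 = 13 days apart. The ANC criterion can be checked from a single value. The more-than-4-days platelet criterion can be checked only where scheduled or extra draws happen to span that time.

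**The case against.** The strongest reply is that Section 20.2 does not say that only these results are recorded. Its general AE definition covers laboratory observations, and Section 20.6.1 requires all AEs to be collected. Where the protocol wants an exclusive rule it writes one: Sections 16.9 and 16.11.1 limit reporting to clinically significant abnormalities, but at Week 16 and after Week 19, outside the DLT window. Section 20.8 also sends a purely laboratory liver criterion to the AE eCRF, so the three conditions are not the sole route. Section 21 itself treats Grade 4 neutropenia as an AE. Investigators see the counts and sit on the Safety Monitoring Committee.

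This stands in part. It rules out saying that such an event will be missed. It does not close the gap: an investigator may record the value, but the one instruction specific to laboratory results does not require it. Section 20.8 shows that the sponsor writes an explicit recording rule when it wants one, and Section 21 has none.

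A reader might also infer that an omitted DLT could still turn a too-toxic result (3 of 6) into an expansion by three patients. The documents do not support that as a live risk. They state that the first Simon stage has been passed, and Part B could open only after the Part A decision. Nor do they show that any event was in fact missed.

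Finally, a difference between AE tables and laboratory grade tables is not in itself an error, since they measure different things. The point concerns only values that Section 21 defines as DLTs.

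**Conclusion.** The conflict between the recording rule and the counting rule is real but narrow. It affects asymptomatic, untreated Grade 4 neutropenia, and Grade 4 thrombocytopenia lasting more than 4 days without transfusion. It is a risk of under-capture.

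Two things remain exposed. One is the reported Part A DLT incidence, by the amounts in Step 3 per omitted event. The other is the Part B Stage 1 set: one reclassified Part A patient would be 1 of 15. The documents give no responder count, so they do not support any claim that the Stage 1 result would change. Section 24.4 does not use DLT status to exclude Part A patients from the Efficacy Evaluable Population, so this point does not reach the Part C response analysis.

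The conclusion assumes that some sites apply Section 20.2 literally. How often that happened, and how often such cytopenias occurred, cannot be known from the documents. The DLT criteria themselves are not in question.

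**What to change.** 1. **SAP 16.1.7 (the part that matters most now).** Add a programmed check of Part A hematology in the DLT window against the value-based Section 21 criteria: ANC below 0.5 × 10^9/L, and platelets below 25 × 10^9/L with duration as far as the draws allow. Reconcile each hit with the AE-form DLT flag before Part A is reported, and list any discrepancy.
2. **Protocol 20.2.** Reconcile it with Section 21 by stating that a laboratory value meeting a Section 21 criterion in the DLT window is recorded as an AE whether or not there are symptoms or any action is taken. This sentence cannot change how past Part A events were entered, which is why the SAP check is needed. No clause for events of clinical interest is needed, because Section 20.8 already puts them on the AE eCRF.

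The cost is one sentence, a small amount of programming and some site queries on data already collected. The reported DLT count may rise, and a Part A patient's status for Stage 1 may have to be revisited.

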# 20.3 Serious Adverse Event (SAE)

All AEs will be evaluated for seriousness. A **serious adverse event** (SAE) is an AE that meets at least one of the following criteria:

- Results in death (NOTE: death is an outcome, not an event)
- Is life-threatening
- Requires inpatient hospitalization or prolongation of an existing hospitalization
- Results in a persistent or significant disability or incapacity
- Results in a congenital anomaly or birth defect
- Additionally, important medical events that may not result in death, be life-threatening, or require hospitalization may be considered SAEs when, based on appropriate medical judgment, they may jeopardize the patient and may require medical or surgical intervention to prevent one of the outcomes listed in this definition. Examples of such events include allergic bronchospasm requiring intensive treatment in an emergency room or at home, blood dyscrasias or convulsions that do not result in hospitalization, or development of drug dependency or drug abuse.

**Life-threatening**, in the context of an SAE, refers to immediate risk of death as the event occurred per the reporter. A life-threatening experience does not include an experience, had it occurred in a more severe form, which might have caused death, but as it actually occurred,

did not create an immediate risk of death. For example, hepatitis that resolved without evidence of hepatic failure would not be considered life-threatening, even though hepatitis of a more severe nature can be fatal. Similarly, an allergic reaction resulting in angioedema of the face would not be life-threatening, even though angioedema of the larynx, allergic bronchospasm, or anaphylaxis can be fatal.

**Hospitalization** is official admission to a hospital. Hospitalization or prolongation of a hospitalization constitutes criteria for an AE to be serious; however, it is not in itself considered a serious adverse event (SAE). In the absence of an AE, a hospitalization or prolongation of a hospitalization should not be reported as an SAE. This is the case in the following situations:

- The hospitalization or prolongation of hospitalization is needed for a procedure required by the protocol. Day or night survey visits for biopsy or surgery required by the protocol are not considered serious.

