#### 16.1.5. AES LEADING TO DEATH

TEAEs leading to death are those events which are recorded as "Fatal" on the Adverse Events page of the CRF.

A summary of TEAEs and TRAEs leading to death by SOC and PT will be prepared.

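### Protocol 20.2 gives two unreconciled rules for hospitalization due to clear progression, so the all-cause SAE tables depend on which sentence a site follows

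*Protocol*

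**What the plan says.** Three consecutive sentences in Protocol 20.2 deal with progression.

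- The first says that clear progression of the primary malignancy "should not be reported as an AE, unless it results in hospitalization or death".
- The second has two clauses. One is general and carries no exception: "Findings that are clearly consistent with the expected progression of the underlying cancer should not be reported as an adverse event". The other turns to admissions and is only permissive: "hospitalizations due to the progression of cancer do not necessarily qualify for an AE".
- The third opens "If there is any uncertainty about a finding being due solely to progression of primary malignancy" and directs that the finding then be reported.

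Protocol 20.3 defines an SAE as an AE that meets at least one listed criterion. Death is one criterion; another is "Requires inpatient hospitalization or prolongation of an existing hospitalization". It also states: "In the absence of an AE, a hospitalization or prolongation of a hospitalization should not be reported as an SAE". It closes with a default that doubt about SAE status is settled in favour of SAE.

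The SAP takes both groups of events from the site's entries on the Adverse Events page of the CRF. Section 16.1.5 begins "TEAEs leading to death are those events which are recorded as" and names the Fatal entry; 16.1.6 identifies SAEs by the Serious entry. Neither section says how progression events are to be handled. SAP 16.2 summarizes and lists deaths from a separate death details page.

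**The concern.** Two sites with identical patients, each admitted for unequivocal progression, could record them differently and both be following 20.2. The first sentence makes the event an AE and hence, through 20.3, an SAE to be reported within 24 hours (Protocol 20.7). The second lets a site record nothing, and it does not say what separates an admission that qualifies from one that does not.

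The incidence of AEs and SAEs is a stated secondary endpoint (Protocol 24.1), and safety is a secondary objective of Parts B and C. The trial has one treatment arm, so there is no control group recorded under the same mixture of practices against which to read the rate. At least 8 sites are planned (Protocol 10.6). Most eligible patients will have progressed on available therapy, and SAE collection continues after treatment stops, so admissions for progression while SAEs are being collected are foreseeable.

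**Working it through.** The plan states no figure on this point, so there is none to reproduce. The check is a comparison of text, followed by a calculation of scale.

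**Step 1. Clear progression with hospitalization.** Under the first sentence of 20.2 this is an AE. The first clause of the second sentence says not to report it and makes no exception. The second clause says the admission may or may not qualify. The wording is permissive, so this is an unresolved inconsistency, not a flat contradiction.

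**Step 2. Does another rule settle it?**
- The uncertainty sentence in 20.2 covers doubt about whether progression is the sole cause. Clear progression carries no such doubt.
- The doubt rule in 20.3 covers doubt about SAE status. In the same section, a hospitalization without an AE is not an SAE, so the question returns to whether 20.2 makes the event an AE.

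Neither rule settles clear progression.

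**Step 3. One patient, two readings.** Take an admission for clear progression with no other AE.

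| | First sentence followed | Second sentence followed |
|---|---|---|
| AE recorded | Yes | Need not be |
| SAE under 20.3 | Yes | No, if no AE is recorded |
| 24-hour report | Yes | No, if no AE is recorded |
| In SAP SAE table | Yes | No, if no AE is recorded |

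**Step 4. Clear progression with death.** The first sentence names death as an exception; the second does not mention death. The specific exception more naturally governs. The remaining difficulty is that the first clause of the second sentence is unqualified and does not acknowledge the exception.

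**Step 5. Which outputs use these entries?**
- Affected: all-cause TEAE, SAE and fatal-TEAE tables.
- Not affected: DLTs, because Protocol 21.0 excludes events clearly due to progression; ORR24, PFS and OS, which do not draw on AE reporting; and the SAP 16.2 death table, which has its own CRF page.
- Little affected: treatment-related tables, because 20.2 lists underlying disease among the non-treatment causes.

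**Step 6. Scale.** Input: 60 patients, the planned maximum (Protocol 10.5). Let k be the number of patients whose only SAE is clear progression. Between recording all of them and recording none, SAE incidence moves by k/60.

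- k = 1: 1/60 = 1.7 points
- k = 3: 3/60 = 5 points
- k = 6: 6/60 = 10 points
- k = 12: 12/60 = 20 points

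The values of k are assumptions. The documents give no rate of progression-related admission, so k cannot be derived from them.

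**The case against.** The best defence is that the sentences can be read together. Protocol 20.3 says that hospitalization is not itself an SAE and exempts several kinds of admission, such as those for protocol-required procedures. The second sentence of 20.2 could be making the same point: the admission alone is not the event. Both doubt rules also lean toward reporting. This narrows the gap but does not close it, because no sentence says when an admission for clear progression qualifies.

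A second argument is that the SAP already shows much of what is needed. SAEs are tabulated by preferred term, so an event recorded as disease progression would be visible, and deaths are summarized independently of AE entry. That stands, and it makes the fix small. It does not help with admissions that were never recorded as AEs.

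It also stands that no between-arm comparison is at risk in a single-arm trial, and that divergent site practice is a possibility the text allows, not something the documents show.

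A reader might go further and infer that the fatal-AE count could run from none to every progression death. The text does not support this: the second sentence never names death, and the first sentence names it as an exception.

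**Conclusion.** The point holds for hospitalization due to clear progression. Protocol 20.2 gives two rules, nothing else in the documents reconciles them, and the SAP carries the result into the reported tables. For death, the exception is the more natural reading, and the second sentence needs only to be aligned with it. The reach is limited to the all-cause TEAE, SAE and fatal-TEAE tables and to 24-hour SAE reporting.

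The supportable size is 1.7 percentage points of SAE incidence per patient whose only SAE is clear progression, on a denominator of 60. A reader might assume that 10–25% of 60 patients (6–15) are admitted or die from progression and infer a shift of 10–25 points. The documents do not support that rate. The inference also requires that none of those patients has another SAE and that recording differs for all of them. Nor does every patient have a 90-day SAE window: under Protocol 20.6.1 it shortens to 30 days after treatment ends if new anticancer therapy is started.

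This is worth correcting because it makes a stated secondary endpoint interpretable, but it does not touch the primary analysis.

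**What to change.** - **Protocol 20.2:** reconcile the sentences into one rule that covers clear progression with hospitalization and with death. The sponsor chooses the rule; what matters is that only one reading is left.
- **Data already entered:** apply the rule through a query to sites, covering admissions for progression whether or not an AE was recorded.
- **SAP 16.1.5 and 16.1.6:** repeat the rule, and tabulate SAEs and fatal TEAEs with and without preferred terms for disease progression.
- **SAP 16.2:** split deaths by whether they were disease related. SAP 5.4 already uses that field from the death details page, so no new data are needed.

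The cost is a wording change in each document, one data query and a few extra rows in planned tables.
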